### **Screening Period (Screening to Treatment Visit)**

Within 14 days prior to treatment visit or at Screening Visit, written informed consent from the parent(s)/legal guardian(s), and subject assent (if applicable), will be obtained before any study-related assessments or procedures are performed. The subject's participation in the trial must be documented in the subject's medical record and all study related evaluations performed at each visit must be clearly documented in source documentation and on electronic case report forms (eCRFs).

Study sites should check the interactive response technology (IRT) for subject age cohort availability before Screening Visit begins. If the subject qualifies, Screening Visit can proceed with the documentation of demographic data, the assessment of study inclusion/exclusion criteria, and past/current medical history. The subject can then be entered into the IRT system to continue screening.

Once IRT has confirmed subject participation, physical and laboratory assessments may be performed ( [Section 8.4](#) ). At this visit, subjects will be instructed to withhold any prohibited medication as applicable ( [Table 6-3](#) ) prior to Treatment Visit (Day 1). The window between Screening Visit and Treatment Visit Day 1 (Screening Period) is up to 14 days.

Throughout the study (from Screening Visit through Follow-up period), subjects will continue to receive their rescue medication (e.g. SABA) and potentially SoC asthma therapy which could be ICS with or without additional controller medication. Leukotriene receptor-antagonists (LTRAs) must be stopped at Screening Visit and in that case ICS should be initiated or up-titrated to the next higher dose as per investigator's judgement; this change of treatment should be allowed to stabilize during the 14 days Screening Period. LTRAs treatment can be continued after End of Treatment (EOT) as per investigators decision.

Rescue medication such as SABAs will not be provided in this study, but may be prescribed by the investigator and used as needed.

### **Treatment period Day 1 to Day 4-8 (Treatment Visit to End of Treatment Visit)**

Eligible subjects meeting all inclusion and exclusion criteria will enter the 4-8-day Treatment Period of the respective cohort.

#### **Treatment Visit (Day 1)**

On Treatment Visit (Day 1), qualifying subjects should have scheduled visit in the morning. Prior to the performance of Treatment Visit (Day 1) clinical evaluations, the investigator will re-assess inclusion/exclusion criteria, adverse events (AEs) serious adverse events (SAEs), Screening Visit laboratory results and the ECG interpretation. If eligible to continue, subjects will have procedures performed as outlined in [Table 8-1](#) , and entered into the IRT system to obtain treatment pack assignment. For remote visits IRT entry into the system will occur prior to home visit.

Subjects will then receive a witnessed dose of fevipiprant CT. Depending on the assigned cohort, the subjects will receive 1 or more CTs. A light breakfast (e.g. average sized serving of cereal, milk, banana, and/or yogurt) should be provided about 30 minutes prior to dosing during the clinic/remote visit. Subjects will be instructed to chew small piece of banana/yogurt followed immediately by CT(s) and then followed with an additional piece of banana/yogurt. Subjects will be encouraged to drink some water thereafter. Time of dosing and confirmation that a light breakfast was given will be recorded on the patient diary card. Subjects will remain in the clinic/remote visit for at least 2 hours for observation after the witnessed dose of fevipiprant. For remote visits the nurse will remain in the home for 2 hour observation.

At this visit, subjects and parent(s)/guardian(s) will be instructed to:

- Give a light breakfast about 30 minutes prior to administration of study drug at the approximate same time each morning of Treatment Day 2 through 1 day prior to EOT.
- CT(s) administration should be done in the following order: chew small piece of banana/yogurt followed immediately by CT(s) and then followed with an additional piece of banana/yogurt.  
Subjects will be encouraged to drink some water thereafter.
- Record the actual time of dosing and confirmation that a light breakfast was given on the patient diary card each day.
- Dosing 1 day prior to EOT should ideally happen approximately 23 h before the planned arrival at the clinic/remote visit on Day 4 to 8 (End of Treatment Visit).
- Withhold study drug the morning of EOT Visit. Study drug will be administered by study site staff/remote nurse in the clinic/home.

Prior to leaving the clinic/home, parent(s)/legal guardian(s) will be dispensed study drug for home administration during the Treatment Period, a study diary card to record time of dosing, and will make an appointment to return to the clinic on EOT Day.

#### **End of Treatment Visit (Day 4 to 8)**

The End of Treatment Visit can only occur after 3 consecutive days of dosing (i.e., as early as Day 4 of dosing).

At the EOT Visit Day, subjects should not take the study drug at home, and arrive at the site or planned remote visit in the morning. Study drug will be taken in the clinic/home, and PK

sampling will occur over 8 hours; the subject and parent/guardian will need to be available to remain in the clinic/home for about 8 to 9 hours.

The scheduling and timing of EOT Visit should ensure dosing of study drug in the clinic/home takes place about  $24 \pm 2$  hours after the last dose of study drug taken at home. On the day prior to EOT, visit study personnel should remind the subject and parent/guardian in a phone call to take study medication at the right time in relation to the scheduled EOT visit. Additionally, PK sampling requires confirmation that study drug was taken for 3 consecutive days prior to EOT Visit. This information must be confirmed by study personnel/remote nurse at EOT Visit by the review of the subject's daily dosing diary. If study personnel/remote nurse cannot confirm that study drug was taken by the subject on 3 consecutive days prior to EOT Visit, the EOT Visit can be rescheduled for +1 to 2 days later. In cases where the subject cannot make the scheduled EOT Visit or has mistakenly taken the study drug at home on the Day of EOT Visit, the Visit can be re-scheduled to the next available clinic/home day.

At the start of the EOT Visit, eligibility to proceed with PK assessments will be confirmed and subjects will receive a light breakfast (e.g. average sized serving of cereal, milk, banana, and/or yogurt) at the study site about 30 minutes prior to dosing. Prior to dosing subjects should be encouraged to empty their bladder in the rest room (not collected for urine PK sampling, but can be used for urine dipstick) in order to get a clear pool of urine post dosing, used for urine PK sampling. Subjects will be administered the final dose of study drug by study staff within approximately 30 minutes after completion of breakfast. Subjects will be instructed to chew small piece of banana/yogurt followed immediately by CT(s) and then followed with an additional piece of banana/yogurt. Subjects will be encouraged to drink some water thereafter. The procedures associated with EOT Visit (including the placement of an indwelling catheter with local anesthetic for blood draws) will be performed in the clinic/home as outlined in [Table 8-1](#). [Section 16.4](#) outlines the PK and vital sign (VS) timing of assessments noting that at time points where multiple procedures occur; the following order is recommended: VS, e.g. PK sampling, laboratory blood draws.

The time of dosing for witnessed dose of fevipiprant CT will be recorded in the eCRF. Throughout the visit, subjects should be encouraged to drink water in order to allow urine production for urine collection.

Blood for PK sampling may be drawn via intermittent venous punctures with topical anesthetic or via the placement of an indwelling catheter with local anesthetic. PK sampling will be obtained as close as feasible to planned times with the actual times of blood draws recorded in source and on the eCRF.

In addition to breakfast, subjects may have food during their time at the clinic/home, but it is recommended that they wait at least 3 hours after dosing to eat.

To avoid the need for an overnight stay at the clinical site, the pre-dose drug concentration values obtained on EOT Visit will also be used as the 24-hour post-dose drug concentration value to calculate AUC0-24,ss. For this reason it is important to have approximately 24 h between the last at home dose and the witnessed dose in the clinic at the EOT Visit.

Upon completion of all EOT Visit study assessments, at the investigator's discretion, the subject may go home.

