### 16.3 Appendix 3: Blood Volume Table

**Table 16-3 Blood volume**

Study phase	Time (h) 	Safety	PK		
			Dose Reference ID	Sample no.	mL
Screening (days -14 to -1)		5			
Treatment Day 1 (Baseline)					
End of Treatment	0 (pre-dose)	5	10  /11	101	1
	0.5		11	102	1
	1		11	103	1
	2		11	104	1
	3		11	105	1
	5		11	106	1
	8		11	107	1
Sub-total blood volume		10			7
TOTAL Blood volume (mL)					17

only one PK sample is collected at pre-dose, but the time difference to the doses on day prior to EOT and EOT day will be derived, requiring 2 dose reference IDs.  
Times are relative to the last dose on Day 4-8.

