2.5.2 Statistical hypothesis, model, and method of analysis

The primary variables, AUC_{0-24h,ss}, C_{max,ss} and CL/F will be analyzed by standard non-compartmental analysis and summarized for Cohort A, through descriptive summary statistics (including mean, SD, CV% mean, Geometric mean, CV% geometric mean, median, minimum and maximum).

Plasma concentrations will be assessed at EOT visit (pre-dose, 0.5, 1, 2, 3, 5, 8h) and will be expressed in mass per volume units. All concentrations below the lower limit of quantification (LLOQ) or missing data will be labeled as such in the concentration data listings. Concentrations below the limit of quantification will be treated as zero in summary statistics and for the calculation of parameters and the pre-dose concentration on EOT visit will also be used as 24 h concentrations to derive AUC_{0-24h,ss}.

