5.7 Rule of exclusion criteria of analysis sets

The following table provides the protocol deviations (PD) and other criteria leading to partial or complete exclusion from analyses sets

Deviation ID	Description of Deviation
Deviations leading to exclusion from all analyses sets	
INCL02A	Subject entered the study without the parent/legal guardian signing the informed consent
INCL02B	Subject entered the study without signing the assent where local law requires assent
Deviations leading to exclusion from PK analysis set	
TRT01	Subject did not receive a total of at least four consecutive, daily doses of study drug

6 Reference

General Clinical Pharmacology Considerations for Pediatric Studies for Drugs and Biological Products, FDA

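### The EOT pre-dose level is entered as the 24 h level without using the recorded gap since the last home dose, and the SAP has no timing-specific rule for gaps outside 22–26 h

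*Protocol*

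**What the plan says.** **Reuse rule.** Protocol Section 3 (End of Treatment Visit) explains that, to avoid an overnight stay, "the pre-dose drug concentration values obtained on EOT Visit will also be used as the 24-hour post-dose drug concentration value". Protocol 12.4.2 makes this an analysis rule, and SAP 2.5.2 keeps it: "the pre-dose concentration on EOT visit will also be used as 24 h concentrations to derive" AUC0-24h,ss. Neither analysis section attaches a condition on elapsed time.

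**Timing control.** Section 3 does ask for a gap: "The scheduling and timing of EOT Visit should ensure dosing of study drug in the clinic/home takes place about" 24 ± 2 h after the last home dose. It gives the reason, that "it is important to have approximately 24 h between the last at home dose and the witnessed dose". Families are told at Day 1 that "Dosing 1 day prior to EOT should ideally happen approximately 23 h before the planned arrival", and staff make a reminder call the day before.

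**Check before sampling.** "Additionally, PK sampling requires confirmation that study drug was taken for 3 consecutive days prior to EOT Visit". The visit may be moved if that cannot be confirmed, if the child cannot attend, or if the dose was taken at home that morning. A gap outside 22–26 h is not among the grounds.

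**Data held.** Table 8-1 records the time of the dose on the day before EOT. Table 16-3, footnote 1, says that "the time difference to the doses on day prior to EOT and EOT day will be derived".

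**Exclusions.** Protocol 12.1 and SAP 2.2 remove subjects whose protocol deviations affect PK data. SAP 5.7 itemises this for the PK set as TRT01 only: "Subject did not receive a total of at least four consecutive, daily doses of study drug". Sensitivity analyses are marked not applicable (protocol 12.4.4, SAP 2.5.4).

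**The concern.** The sponsor's own reasoning makes the method depend on the gap, yet the analysis text never uses it. The pre-dose sample is a 24 h level only if the home dose was taken 24 h earlier. After a later home dose the sample is too high, so AUC0-24h,ss is overstated and CL/F understated. After an earlier home dose the reverse holds. Both parameters are primary.

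No timing criterion says what happens to a child at, say, 18 h. Followed as written, SAP 5.7 keeps that child in the PK set and SAP 2.5.2 enters the 18 h level at 24 h. With six profiles, the choice between keeping and dropping a child would otherwise be made after the data are seen.

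**Working it through.** **1. The plan's own precision figure.** Inputs from protocol 12.7.1: n = 6, CV 31%, 80% probability.

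- σ = √ln(1 + 0.31²) = 0.3029
- Half-width on the log scale = t(0.975, 5) × σ × √(χ²(0.80, 5)/5) / √6 = 2.571 × 0.3029 × √(7.289/5) / 2.449 = 0.384
- exp(±0.384) gives 68.1% to 146.8%, which matches the stated 68% to 147%.

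**2. Model for the timing error.** Inputs:

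- Accumulation of about 1.3-fold (protocol 4.2, adults): k = −ln(1 − 1/1.3)/24 = 0.0611/h, half-life about 11.3 h.
- Tmax 2 to 2.5 h (protocol 4.2, capsules); 2.25 h used, giving ka = 1.477/h.
- Sampling at 0, 0.5, 1, 2, 3, 5 and 8 h, with the linear trapezoidal rule (protocol 8.5.1).
- Assumption: one-compartment oral model with superposition of doses.

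With an exact 24 h gap (dose/volume set to 1) the levels are 0.313, 0.817, 1.037, 1.146, 1.117, 0.998 and 0.832, with 0.313 reused at 24 h. Then AUC = 16.99.

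**3. Weight of the reused value.** The 8–24 h segment is 8 × (0.832 + 0.313) = 9.16, or 54% of AUC. The reused value supplies 8 × 0.313 = 2.50, about 15%. The measured 8 h level supplies 8 × 0.832 = 6.66, about 39%.

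**4. Error by gap, against an exact 24 h.** Case L mistimes only the last home dose. Case W shifts the whole home schedule. CL/F = dose/AUC, so its error is the reciprocal. The adjusted value at 24 h uses the child's own points:

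λ = ln(C8/Cpre)/(gap − 8), C24 = Cpre × exp(−λ × (24 − gap)).

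| Gap | Case | Pre-dose | AUC | CL/F | AUC after adjustment |
|---|---|---|---|---|---|
| 18 h | L | +34.1% | +12.1% | −10.8% | +4.8% |
| 18 h | W | +44.3% | +15.7% | −13.6% | +8.3% |
| 22 h | L | +10.0% | +3.5% | −3.4% | +1.6% |
| 22 h | W | +13.0% | +4.6% | −4.4% | +2.6% |
| 26 h | L | −8.8% | −3.1% | +3.2% | −1.5% |
| 26 h | W | −11.5% | −4.1% | +4.3% | −2.4% |

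Example (22 h, case L): Cpre = 0.344 and AUC = 17.59, so 17.59/16.99 = 1.035. λ = 0.0646/h, C24 = 0.344 × exp(−0.129) = 0.302, and AUC becomes 17.26, or +1.6%.

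The adjustment removes about 40% to 55% of the in-window error. The rest is carry-over in the 0–8 h samples, which reuse does not cause.

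**5. Sensitivity to half-life.** With assumed half-lives of 6 and 20 h (case W), the AUC error at 22 h is +3.3% and +4.1%, at 26 h −2.6% and −3.8%, and at 18 h +12.8% and +13.1%.

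**6. Effect on the summaries.** Gaps spread uniformly over 22–26 h (case W) give a mean AUC bias of about 0.1% and add about 2.5% CV: √(31² + 2.5²) = 31.1%. The range in step 1 becomes about 68.0% to 147.0%. One child in six at 22 h moves the geometric mean by 1.046^(1/6) − 1, about 0.8%. One at 18 h moves it by 1.121^(1/6) − 1 = 1.9% to 1.157^(1/6) − 1 = 2.5%.

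**7. Cost of dropping a child.** With n = 5, step 1 becomes 2.776 × 0.3029 × √(5.989/4) / √5 = 0.460, giving 63% to 158%.

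**The case against.** The strongest reply is that the plan saw this risk and controls it in conduct: a stated window, a morning-dosing instruction, a reminder call and a recorded dose time. That stands. A reader might infer that the protocol accepts any gap. It does not: a child dosed at home the evening before would breach both the morning instruction and the 24 ± 2 h window. The gap is in the analysis rule.

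The second reply is that the general clause on deviations affecting PK data covers a mistimed child. It could, but it gives no threshold, and SAP 5.7 turns it into TRT01 alone. It would also remove the whole child, including Cmax,ss, which the reuse does not touch.

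The third is that protocol 8.5.1 uses actual sampling times. No text reconciles that with fixing the pre-dose level at 24 h.

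Three stronger readings are also not supported:

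- That the reused value determines about half of exposure. The 8–24 h segment is about half; the reused value supplies about 15%.
- That the primary endpoints are biased. In-window errors take either sign, and the documents report no mistimed child.
- That correcting the SAP would change the Cohort B dose or size. The SAP post-dates termination, when five Cohort B children had already been treated.

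Phase III dose selection was to rest on population PK modelling, not on this non-compartmental summary.

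**Conclusion.** The point holds in limited form. The plan sets a window and collects the gap, but the rule for AUC0-24h,ss and CL/F ignores it, and no listed exclusion refers to hours. Per child, the AUC error is +3.5% to +4.6% at 22 h, −3% to −4% at 26 h and +12% to +16% at 18 h, with CL/F opposite. In-window error is negligible beside a 31% CV. Off-window error is large enough to need a rule fixed in advance.

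Cmin,ss is the more sensitive parameter, about ±10% at the window edges, but it is secondary. It moves because the sample itself is mistimed, not because it is reused.

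These sizes rest on a one-compartment shape and adult accumulation, neither of which the documents confirm in children. The reach is six Cohort A profiles, summarised descriptively.

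**What to change.** In SAP 2.5.2, as a stated change from protocol 12.4.2:

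1. Use the recorded hours since the last home dose to adjust the 24 h value log-linearly from the child's own 8 h and pre-dose points, before computing AUC0-24h,ss and CL/F.
2. For any gap outside 22–26 h, flag the child in the listings and give the AUC0-24h,ss, CL/F and Cmin,ss summaries with and without that child.
3. Keep Cmax,ss and Tmax,ss for all children.

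The cost is one derivation and one extra summary, on data already collected. The adjustment leaves about half of the in-window AUC error, because carry-over in the 0–8 h samples remains. Showing both summaries is preferable to outright exclusion, since losing one of six children widens the 80%-probability range from 68–147% to about 63–158%.

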### **Follow-up Period (Phone call to Parent/Gurdian)**

Following the treatment period or discontinuation (last dose of study drug), a follow-up period of 30 days, investigational drug free, will assess any safety-related adverse events.

## **4 Rationale**

### **4.1 Rationale for study design**

This is an open-label study with an 8 day preferred treatment period to assess pharmacokinetics and safety of 2 different doses levels of fevipiprant CT. The 2 dose cohorts (A and B) will be studied consecutively, to allow to assess low dose data before escalating to a higher dose level in this first study in children of 6 to < 12 years. After cohort A an interim analysis will decide the fevipiprant dose and number of subjects tested in cohort B. By this a sufficiently good definition of the primary pharmacokinetic endpoint and an adequate exposure in the high dose group is supported. As the primary objective of the study is a pharmacokinetic assessment, the open-label design is considered appropriate. A population pharmacokinetics (PopPK) modeling approach will be used to integrate data from this study with adult and adolescent PK data to support the pediatric Phase III dose selection. The PK sampling in this study (i.e. from pre-dose to 8 h post dose at steady state) is adequate to inform the PopPK model. This is the first fevipiprant study in this age range and final dose selection requires the data obtained in this study. Therefore, pediatric Phase III dose level may not be identical to one of the dose levels tested in this study. However, the flexibility in selecting the high dose based on 75 mg/day data will allow an appropriate range to be covered.

#### **4.1.1 Rationale for choice of background therapy**

Subjects will continue to receive their rescue medication (e.g. SABA) and potentially SoC asthma therapy throughout the study (from Screening Visit through Follow-up period). Since the purpose of the study is to assess PK, safety and tolerability of fevipiprant CT there is no need to alter the background medication (with exemption of LTRAs which could potentially interfere with the PK analyses of fevipiprant).

### **4.2 Rationale for dose/regimen and duration of treatment**

The ongoing Phase III program in asthma tests the dose levels of 150 and 450 mg/day once daily in adults and adolescents down to age 12. Dose levels for Phase III studies in subjects < 12 years of age are planned to be selected to provide systemic fevipiprant exposure similar to that of dose level finally selected for treatment of adults and adolescents (either 150 or 450 mg/day).

Since the adult dose of fevipiprant is once daily, a once daily regimen for fevipiprant will also be used in this initial trial to obtain pharmacokinetic exposure of fevipiprant in subjects aged 6 to <12 years. It is known that in adults, steady state exposure is reached within 4 days of once daily dosing with little (~ 1.3 fold) accumulation. Based on adult data a similar duration of dosing to obtain steady state information in subjects 6 to <12 years is also planned.

Pharmacokinetic sampling at steady state in 6 to <12 years old subjects can occur as early as 4 days after dosing as long as study personnel can confirm that study drug was taken by the subject

on 3 consecutive days prior to End of Treatment Visit. In order to introduce flexibility in the protocol a visit window is included, which allows the pharmacokinetic sampling at steady state to occur anywhere from 4-8 days after dosing. In case study personnel cannot confirm that study drug was taken by the subject on 3 consecutive days prior to EOT Visit (which can occur anywhere from Day 4-8), the EOT Visit can be rescheduled for +1 to 2 days later. In addition, this duration will allow the first and last doses of study medication requiring visits at the hospital/clinic to occur during the weekend or on a designated day in the week most convenient to the family.

Based on the current understanding of the dose-effect and dose-safety relationship, it is assumed that children aged 6 to < 12 years can be treated by 1 fixed dose level. The dose levels of 75 mg and potentially 225 mg selected for this study are expected to provide an exposure in children aged 6 to < 12 years which is comparable to the 150 mg and 450 mg dose levels in adults. The dose levels were derived by weight-based allometric scaling, also considering physiologically-based PK modeling results. The bioavailability of the CT used in this study relative to the film-coated tablet (FCT) used in adults and adolescents was assessed in adults and was close to one (~ 1.18). If the exposure at 75 mg/day is relevantly lower or higher than expected, the dose level in the high dose group will be adjusted accordingly considering available dose strength of CTs (e.g. to 150 mg (2\*75 mg) or 300 mg (225 + 75 mg)).

In a preliminary food effect assessment with capsules, food had no clinically relevant impact on the PK of fevipiprant: a delay in median Tmax from 2 to 2.5 h was observed with a high fat meal and based on the point estimate Cmax was 7% reduced. Fevipiprant is dosed independent of meals in Phase III studies in asthma. Although no major effect of food on fevipiprant PK is expected, a light breakfast should be provided before dosing on all study days to standardize food effects across the study population and, hence, minimize any potential effect of meal conditions on PK variability as well as to support the well-being of children during blood collection.

Fevipiprant has a good safety profile in populations studied to date at total daily doses up to 500 mg/day given for durations of up to 12 weeks and at doses of 1800 mg/day administered for a duration of up to 1 week; the maximal tolerated dose of fevipiprant in humans has not been identified thus far.

